## Methods:

**Overall study design.** We will use a two-group cross-over design. Each group will complete three conditions, each lasting one week. 12 participants will be randomized to one of the two groups. Group one (n=6) will receive one-week placebo, one-week washout, and one-week SUVO. Group two (n=6) will receive one-week SUVO, one-week washout, and one-week placebo. During the washout period, the participants will not receive any pills. Eligibility criteria and baseline measures will be collected on Day 0 before the start of week one. Participants will come to the clinic once a week on Monday for 4 weeks. On Day 1 (Monday) of the first week, the participants will receive their medication and actigraphy watches. Each following Monday, they will complete self-report and drug use measures, as well as the laboratory tasks (cold pressor and EEG). Table 1 outlines the schedule of assessments. We will aim to enroll a total of 16 participants to complete 12, with dropouts being replaced, if possible.

**Participants, Recruitment, and Setting.** The participants will consist of non-treatment-seeking individuals meeting DSM-5 criteria for MA use disorder. All participants will be between the ages of 18-45 and fluent in English. IRB NUMBER: HSC-MS-22-0796 IRB APPROVAL DATE: 10/09/2023

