**Cue Reactivity/Craving (LPP).** The late positive potential (LPP) is an event-related potential component thought to reflect the motivational relevance of visual stimuli. The LPP to drug images is enhanced in drug users compared to controls, is correlated with craving, and tracks with abstinence, thus serving as an objective measure of cue reactivity/cue-induced craving. EEG will be collected on test days prior to the cold pressor task. The Picture Viewing Task will be used to elicit the LPP. Suvorexant might lead to decrease drug use through reducing reactivity toward drug cues. Therefore, the picture viewing task will provide this neural assessment of cue reactivity. In the task, the participants view images in four categories, pleasant, unpleasant, methamphetamine, and neutral. The other image categories are necessary, so that we can ensure the brain reactivity is specifically in response to drug images and not just salient images. This is a standard task used in the EEG literature and a meta-analysis shows drug users have an increased

response to drug images with a large effect size.

**Cue Reactivity/Craving (Self-Report).** The Brief Substance Craving Scale (BSCS) will be used to assess current MA craving. The BSCS will be assessed on each test day prior to laboratory tasks.

**Safety/Side Effects.** A 31-item questionnaire will be administered on each test day to assess side effects and adverse events. The Colombia Suicide Severity Rating Scale (CSSRS) and Beck's Depression Inventory (BDI) will be administered at each visit per NIH guidelines. Breath alcohol concentration will also be assessed at each visit to assess for current intoxication.

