### Data Analytic Strategy:

**Overview.** Analyses will primarily rely on generalized linear modeling (GLM) for cross-sectional analyses and generalized linear mixed modeling (GLMM) for longitudinal analyses. This approach allows for various outcome distributions and multilevel data. All models will account for repeated observations with via the best-fitting structure of level-2 intercepts/slopes. We will aim to collect full data on 12 participants. Other participants who drop out or are withdrawn will be excluded from analyses, depending on how much data we are able to collect. If only a few data points are missing, generalized linear mixed modeling will natively handle missing outcome data. GLMM natively handles missing data by allowing unequally spaced observations between participants; any other issues related to missing data will be handled via explicit modeling of missingness or imputation. Analyses will be performed in R^72 via packages lme4, rstan, and brms. **Confounders:** Preliminary data analyses will inspect relationships between sample characteristics, predictors, and outcomes via GLMM. Variables that demonstrate a relationship with both the predictor and outcome in a model meet criteria for being potential confounders and yield models with and without covariate adjustment. We report the simpler model if inferences are not affected by these covariates and report both models otherwise.

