**Inference:** Analyses will be run in parallel frequentist and Bayesian models. Frequentist results yield the probability of the data (or data more extreme), given the null hypothesis, while Bayesian results directly yield the probability of an alternative hypothesis. Weakly informative priors will be used for all Bayesian analyses in order to emphasize the influence of the present data. **Multiplicity:** All *a priori* frequentist models will be evaluated at the  $\alpha=0.05$  (two-tailed) significance level, and will employ false discovery rate (FDR) to control for Type I error across any *post hoc* analyses. Bayesian models will be evaluated via PP threshold guidelines in the literature suggesting that PP = 75% to 90% indicates moderate evidence, PP = 91% to 96% indicates strong evidence, and PP = 97% or above indicates very strong to extreme evidence. **Assumptions:** Posterior predictive checking, scale reduction factors ("rhat"), and effective sample size will be used to evaluate Bayesian assumptions. Evaluation for frequentist models will use graphical evidence and statistical tests.

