### Specific Hypothesis Testing.

**Aim 1:** GLMM for repeated measures will separately model each outcome measure as a function of treatment condition, with Level-2 effects included for best fit. Outcomes will include measures of sleep (H1a: actigraphy; self-report sleep quality; EEG), acute stress reactivity (H1b: physiological responses; subjective ratings) and cue reactivity/craving (H1c: LPP to methamphetamine images; self-report craving)

**Aim 2:** Descriptive statistics will evaluate the frequency of adverse events (AEs) and severe adverse events (SAEs) between and within conditions. Logistic regression will evaluate presence (vs. absence) of specific AEs as a function of condition.

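### With about 12 participants, the planned logistic regression of specific AEs has no rule for a condition with zero events, where its default Wald p is near 1 whatever the imbalance

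*Combined protocol and SAP*

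**What the plan says.** Under Specific Hypothesis Testing, Aim 2 has two parts. The first is descriptive: "Descriptive statistics will evaluate the frequency of adverse events (AEs) and severe adverse events (SAEs) between and within conditions". The second is a model: "Logistic regression will evaluate presence (vs. absence) of specific AEs as a function of condition". No test statistic (Wald or likelihood ratio), penalty, exact method or rule for empty cells is given.

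Three other places bear on this.

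- **Data source.** Measures, Safety/Side Effects: "A 31-item questionnaire will be administered on each test day to assess side effects and adverse events". There could therefore be up to 31 specific items to model.
- **Sample size.** Methods: "12 participants will be randomized to one of the two groups", in a crossover with six per sequence; and "We will aim to enroll a total of 16 participants to complete 12, with dropouts being replaced, if possible". Data Analytic Strategy, Overview: "We will aim to collect full data on 12 participants".
- **General rules.** Data Analytic Strategy: "All models will account for repeated observations", with lme4, rstan and brms as the named packages; and "Analyses will be run in parallel frequentist and Bayesian models", with weakly informative priors whose distribution and scale are not stated.

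**The concern.** An AE that appears on one condition and never on the other is the clearest pattern a safety comparison can show. It is also the pattern for which unpenalised logistic regression has no finite estimate. The likelihood keeps rising as the log odds ratio grows, the software stops at an arbitrary large value, the standard error is enormous, and the Wald statistic falls towards zero. The printed p then ranks imbalances in the wrong order, with a complete split looking like no evidence and a slightly less complete one looking significant.

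At stake is how Aim 2 reads. A p near 1 beside a 6-to-0 or 8-to-0 split could be taken as reassurance in a study meant to supply preliminary safety evidence for a later grant. The frequentist and Bayesian results could also contradict each other, and the plan does not say which governs.

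**Working it through.** The plan gives no figure for the AE analysis; its Sample Size and Power section covers only a normally distributed outcome. There is therefore nothing of the plan's own to reproduce here.

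**Inputs.** From the documents: 12 participants, each observed on SUVO and on placebo; logistic regression on condition; lme4 for mixed models; two-sided alpha of 0.05. Assumed, because the documents give no AE rates: placebo 0/12 with k/12 on SUVO, and true rates from 1% to 30%.

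**Step 1: a table with no empty cell.** For 1/12 versus 8/12:
- log OR = ln(8/4) − ln(1/11) = 0.693 + 2.398 = 3.09
- SE = √(1/8 + 1/4 + 1/1 + 1/11) = √1.466 = 1.21
- z = 3.09/1.21 = 2.55, so Wald p = 0.011

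**Step 2: empty the placebo cell.** For 0/12 versus 8/12 the placebo log odds is ln(0/12), which is minus infinity, and the SE contains 1/0. R's glm stops at an estimate of 20.3 with SE about 3,100 and p = 0.995. With a tighter convergence tolerance the SE was about 13,900 and p = 0.999. The SE is an artefact of when the algorithm stops; the conclusion is not.

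**Step 3: all methods with placebo at 0/12.**

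| Method | SUVO 4/12 | SUVO 6/12 | SUVO 8/12 |
|---|---|---|---|
| Wald p, glm | 0.995 | 0.995 | 0.995 |
| Wald p, glmer with random intercept | 1.00 | 0.97 | 0.98 |
| Likelihood-ratio p, same glm | 0.012 | 0.0013 | 0.0001 |
| Firth penalised likelihood-ratio p | 0.035 | 0.005 | 0.0004 |
| Exact McNemar p = 2 × 0.5^k | 0.125 | 0.031 | 0.008 |
| Bayesian P(effect > 0), N(0, 2.5) priors | 0.973 | 0.997 | >0.999 |
| Bayesian P(effect > 0), N(0, 1) prior on effect | 0.916 | 0.978 | 0.996 |

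The glmer standard errors were about 1.9 × 10⁷, 916 and 2,048, with singular-fit and Hessian warnings at 8/12. With complete pairs and no placebo events, every SUVO event is a one-way discordant pair, so the McNemar formula needs no further assumption. The likelihood-ratio, Firth and Bayesian rows ignore pairing, and the priors are assumed.

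**Step 4: how often a cell is empty.** With true rate p, q = P(0/12) = (1 − p)^12. If both conditions share that rate and are independent, P(at least one empty) = 1 − (1 − q)² and P(exactly one empty) = 2q(1 − q).

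| True rate | q | At least one empty | Exactly one empty |
|---|---|---|---|
| 1% | 0.886 | 99% | 20% |
| 5% | 0.540 | 79% | 50% |
| 10% | 0.282 | 49% | 41% |
| 20% | 0.069 | 13% | 13% |
| 30% | 0.014 | 3% | 3% |

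Where both are empty there is no imbalance to miss. The last column is the one in which a Wald p could mislead.

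**The case against.** A reader might infer that the most one-sided AE imbalances will be reported with p near 1, and that the safety aim would miss them. The documents do not support that.

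- **No Wald test is specified.** A likelihood-ratio test on the same model gives 0.012, 0.0013 and 0.0001 at 4/12, 6/12 and 8/12. This stands, though it is only a partial answer: as run it ignores pairing, and it is liberal at this size (0.012 against an exact paired 0.125 at 4/12).
- **The Bayesian model is already planned.** A weakly informative prior is a standard remedy for separation, and under the assumed N(0, 2.5) priors all three splits reach the top band of the plan's own posterior-probability scale. This also stands. What remains is that Aim 2 does not restate the Bayesian model, no prior scale is given (at 4/12 the result moves from the plan's strong band at 0.916 to its top band at 0.973), and no rule says which analysis governs.
- **Counts will be shown.** Aim 2 commits to frequencies by condition, so a 6-to-0 split would be visible.
- **The aim is exploratory.** Participant protection rests on weekly AE review, the AE log and the monitoring committee, not on this p value.

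A reader might also infer that most specific AEs will have an empty condition. That depends on rates the documents do not give: it would hold for items with rates below about 10%, and not for common ones.

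**Conclusion.** The point holds in a limited form. The frequentist part of Aim 2 names a method whose default output breaks down when one condition has no events, and the plan has no rule for that case. If Wald p values are used, p lies between 0.97 and 1.00 for every split examined from 4/12 to 8/12 against 0/12, with or without a random intercept, while 1/12 against 8/12 gives 0.011. Under equal rates and independence, an empty SUVO or placebo cell is close to certain at a 1% rate, about even at 10% and rare at 30%.

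The consequence is limited to the frequentist results of an exploratory aim. The imbalance would still appear in the AE frequencies and in the parallel Bayesian model. The figures rest on complete data for 12 participants, on assumed AE rates, and on assumed priors for the Bayesian rows.

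**What to change.** Amend the Aim 2 text in the SAP before unblinding:

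1. State that Wald p values from unpenalised logistic regression will not be used for specific AEs.
2. Report n/N per condition for each AE with exact 95% intervals. For 0/12 the upper limit is 1 − 0.025^(1/12) = 26.5%, which shows how little a zero count excludes.
3. Name one reported between-condition estimate: the Bayesian logistic mixed model with its prior distribution and scale written down, or Firth-penalised logistic regression.
4. Optionally add exact McNemar, SUVO versus placebo, as a paired supplement.

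No new data or visits are needed. There are statistical costs. A penalised or Bayesian estimate is shrunk and depends on the stated penalty or prior. A simple Firth fit ignores pairing. Exact McNemar takes no covariates, leaves out the washout assessment, and cannot reach 0.05 with fewer than six one-way discordant pairs (five to none gives 2 × 0.5^5 = 0.0625), so it should not be the lead analysis.

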**Study Medication (suvorexant).** Suvorexant (BELSOMRA®) is an orexin receptor antagonist indicated for the treatment of insomnia, characterized by difficulties with sleep onset and sleep maintenance. Recommended dose is 10 mg, 1x per night taken within 30 minutes of going to bed, with at least 7 hours of planned time before awakening. If the 10 mg dose is well tolerated but not optimally effective, it can be increased but not to exceed 20 mg once daily. Medication is taken PO, with dosage in tablets of 5, 10, 15, and 20 mg. Contraindicated in patients with narcolepsy. Precautions include daytime somnolence; dose-related risk of impaired alertness and motor coordination, including impaired driving; patients taking 20 mg should be cautioned against next-day driving; nighttime “sleep-driving” and other complex behaviors while out of bed and/or not fully awake; worsening of depression or suicidal thinking; compromised respiratory function; sleep paralysis, hypnagogic/hypnopompic hallucinations. Risk of the above symptoms increases with use of CNS depressants and alcohol. In obese women (BMI > 30), there is increased risk of exposure-related adverse effects. Belsomra® is a schedule-IV compound with mild/modest abuse-potential in the same class as existing sleep medications and anxiolytics. The most common adverse reactions include somnolence and slowed motor coordination. Not recommended for use in patients taking strong CYP3A inhibitors, efficacy may be reduced, or for patients with severe hepatic impairment. Based on animal data, Belsomra® may cause fetal harm.

**Psychometric Testing.** Items on certain psychological/psychiatric questionnaires and interviews might be perceived as personally discomforting to some subjects.

**Actigraphy.** Participants may experience mild discomfort while acclimating to wearing the device during sleep.

**EEG Task.** The EEG may lead to redness or skin irritation where the sensors are placed. This will almost always disappear after a few hours. The images that the participants will view will contain sexual and violent images (including erotic scenes and mutilated bodies) and may upset some participants. Viewing drug images can induce craving.

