The following procedures will be taken to safeguard against adverse medication events: (1) careful initial intake evaluation to determine eligibility based on inclusion/exclusion criteria; (2) thorough physical evaluation prior to treatment, consisting of physical examination, standard laboratory tests, electrocardiogram, toxicology screen, pregnancy test, and vital signs; (3) repeated tests during treatment; (4) daily monitoring of pill taking via CAROMA, returned pill counts, and self-report; (5) weekly review of adverse events and medication compliance; (6) regular evaluation by the study physician ([name]). Specific criteria will be used to exclude potential subjects for whom any of the study medications is contraindicated. Any abnormal physiological, psychological, or behavioral event will be evaluated and, if indicated, will result in the subject's removal from the study.

We will use an Adverse Event Log (AEL) based on NIDA SAFTEE procedures. The AEL will record the duration, severity, and frequency of any adverse events, signs, and symptoms. An evaluation will be made as to the event's relationship to the study drug(s), scaled as unrelated, unlikely, possible, and probable. The AEL will be included in the report to DSMB.

Subjects will be monitored regularly for compliance with the study requirements, including the dosing regimen and breath alcohol testing upon arrival at the laboratory each day of testing. Written and verbal information about the medication will be given to all participants. This information will remind the subject to: (1) take food shortly after medication if needed to relieve gastric irritation; (2) inform the treatment research clinic nurse or physician of any over-the-counter and prescription medication taken, especially: cough medication, diarrhea medication, narcotic medication; (2) notify treatment research clinic nurse or physician of any side effects that persist or worsen. The study physician, nurse, and PI will review cases involving clinical deterioration of increased symptomatology or substance abuse. Appropriate actions will be taken, including study termination with proper referral.

**Behavioral and Psychometric Testing.** The participants do not have to answer any questions they do not feel comfortable answering and can not take part in the study.

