3. Adverse events (AE) will be reported to the UT-CPHS on an annual basis. Serious adverse events will be reported immediately (verbally within 24 hours) to the UT-CPHS and the Monitoring Committee. A written report will follow as soon as possible but in no more than three days. The written report will be in the format required by the local IRB and will contain information regarding the date of the AE, description of the AE, severity rating (Grade 1 to 4), assessment of cause, whether the AE indicates an increased risk for current or future subjects, and whether changes to the informed consent form are necessary.

4. We will also use an ongoing Adverse Event Log (AEL) based on NIDA SAFTEE procedures. The AEL will record the duration, severity, and frequency of any adverse events, signs, and symptoms. An evaluation will be made as to the event's relationship to the study drug(s), scaled as unrelated, unlikely, possible, and probable. The AEL will be included in the report to DSMB.

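### Aim 2 tests each adverse event only as present or absent although severity is logged, so a complaint present in both weeks but worse on SUVO does not count; the loss grows with the placebo-week rate

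*Combined protocol and SAP*

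**What the plan says.** Aim 2 in Specific Hypothesis Testing has two sentences. The first is descriptive: "Descriptive statistics will evaluate the frequency of adverse events (AEs) and severe adverse events (SAEs) between and within conditions". The second is the only inferential safety analysis: "Logistic regression will evaluate presence (vs. absence) of specific AEs as a function of condition".

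More than presence is collected. Under Adequacy of Protection Against Risks, "The AEL will record the duration, severity, and frequency of any adverse events, signs, and symptoms", and item 4 of the Data Safety and Monitoring Plan repeats this. Neither place gives the log's severity scale. A grade from 1 to 4 appears only in item 3 of that plan, for the written report that follows a serious event. Under Measures (Safety/Side Effects), "A 31-item questionnaire will be administered on each test day to assess side effects and adverse events", with no response scale stated.

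The design is a two-sequence crossover: "12 participants will be randomized to one of the two groups", and "We will aim to enroll a total of 16 participants to complete 12". The overview of the Data Analytic Strategy has every model account for repeated observations, so the logistic regression is presumably a paired or mixed one. No section plans a comparison of graded severity between SUVO and placebo, and none gives a reason for the dichotomy.

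**The concern.** Each participant is their own control. Someone with a mild complaint in the placebo week and a severe one in the SUVO week is coded 1 and 1. The difference is 0, the same as for someone whose complaint did not change. Such a pair contributes nothing to a conditional (paired) comparison and almost nothing to a mixed logistic one.

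Aim 2 is to describe the side-effect profile of SUVO in what the Medication section calls its first study in methamphetamine users, and the work is meant to support a later grant. Under Potential Risks, "The most common adverse reactions include somnolence and slowed motor coordination". If such complaints also have a background rate in the placebo week, a real worsening could be logged and still leave the planned test showing no difference.

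**Working it through.** **The plan's own figure.** No power is given for Aim 2 or for any adverse event. The one power statement (Sample Size and Power) is 80% at f = 0.59 with N = 12, 3 measurements, r = 0.15 and two-sided alpha 0.05, for one normal outcome. It reproduces as a between-groups repeated-measures F test: lambda = f²·N·m/(1+(m−1)r) = 0.3481 × 36/1.30 = 9.64 on 1 and 10 df, power 0.799. It does not bear on this point except as a source for r and a benchmark shift.

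**Inputs.** From the documents: 12 SUVO/placebo pairs, two-sided 0.05, r = 0.15. Assumed: placebo-week rates, the SUVO shift in latent severity, and the grade mix among those affected.

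**Step 1: what the binary test needs.** Only pairs with the complaint in exactly one week count. For k such pairs all in one direction, the exact two-sided p is 2 × 0.5^k. This gives 0.0625 for k = 5 and 0.031 for k = 6, so at least 6 of the 12 pairs must be discordant and all must agree. The mid-p version halves these values and needs 5.

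**Step 2: information kept.** Latent normal severity was cut into none/mild/moderate/severe, with a 0.8 SD shift, correlations from 0.15 to 0.7, two grade mixes and 5,000 trials per setting. Information kept is (mean/SD)² of the binary difference divided by the same quantity for the graded difference. The power columns use exact tests: McNemar for the binary difference and sign-flip for the graded one.

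| Placebo-week rate | Information kept by presence/absence | Power, binary | Power, graded |
|---|---|---|---|
| 10% | 96–103% | 0.03–0.05 | 0.07 |
| 20% | 82–95% | 0.10–0.13 | 0.19–0.27 |
| 40% | 59–79% | 0.15–0.17 | 0.31–0.53 |
| 60% | 39–60% | 0.07–0.10 | 0.33–0.61 |
| 80% | 21–35% | about 0.01 | 0.32–0.58 |

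The loss is therefore 5–18% at a 20% rate, 21–41% at 40%, 40–61% at 60% and 65–79% at 80%. At 80%, 37–41% of pairs have the complaint in both weeks but worse on SUVO. Only 17–22% are discordant, which is 12 × 0.17 = 2.0 to 12 × 0.22 = 2.6 pairs, against the 6 needed.

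**Step 3: power at the plan's r = 0.15.** Mid-p sign-flip tests, grade mix 60/30/10%, 2,000 trials per cell (Monte Carlo error about 1 point). The 1.2 SD shift is about 2 × 0.59.

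| Placebo-week rate | 0.8 SD, binary vs graded | 1.2 SD, binary vs graded |
|---|---|---|
| 10% | 12% vs 14% | 42% vs 49% |
| 30% | 27% vs 36% | 57% vs 71% |
| 50% | 26% vs 42% | 47% vs 76% |
| 70% | 12% vs 43% | 20% vs 77% |

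The gain is 2 to 7 points at a 10% rate, 9 to 29 points at 30–50%, and 31 to 57 points at 70%. The false-positive rate of the graded test is at most 4.9%.

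**Step 4: less favourable settings** (mid-p, r = 0.15).
- 0.5 SD shift: about 11% vs 14% at a 30% rate and 12% vs 19% at 50%.
- 0.8 SD, mostly mild grades (85/12/3%): 27% vs 31% and 23% vs 37%.
- The same with 30% of grades misrated by one level: 29% vs 31% and 25% vs 34%.

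The gain shrinks but does not reverse.

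**The case against.** A reader might infer that most of the paired information on common side effects is lost. The documents do not support that as a general statement. They give no adverse event rate for either week, and Step 2 shows a loss of that size only at the top of an assumed range. The Background reports poorer sleep quality in this population, which is not the same as next-day somnolence or slowed coordination, and sleep disorders are an exclusion. Nor do the documents say whether a complaint that predates treatment is logged in the placebo week. If only new or worsened complaints are logged, the pattern of presence in both weeks becomes rarer. This part of the objection stands.

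Severity is not wholly ignored. The descriptive sentence counts severe events by condition, and the log goes to the monitoring committee. But that count is descriptive, its abbreviation may mean serious rather than severe, and it misses a change from mild to moderate.

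A reader might also assume that the log already carries grades 1 to 4. It may not, because that scale is attached only to the written report. A scale has to be stated before a graded analysis is possible.

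The simulations use exact paired tests as stand-ins. They evaluate neither the planned logistic model nor a cumulative-logit one, and with 12 people the latter could be unstable when grades are sparse. At moderate shifts the graded test is underpowered too. Finally, Aim 2 is exploratory, power is offered only as due diligence, and no section treats a non-significant result as proof of safety. These points limit the weight of the concern. They do not give a reason to discard recorded severity in the one comparison that is tested.

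**Conclusion.** The point holds in a conditional form. The only inferential adverse event analysis reduces each event to presence or absence, although severity is logged, so a complaint present in both weeks but worse on SUVO adds nothing to the paired contrast. The loss is small for events uncommon on placebo and moderate at placebo-week rates of about 30–50%. It covers most of the information only when a clear majority have the complaint on placebo: 40–61% is lost at a 60% rate and 65–79% at 80%. In the settings tried, the graded comparison had at least the power of the binary one and held its error rate below 5%.

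All of these sizes rest on assumed rates, shifts and grade mixes. The stronger inference, that the safety analysis as a whole is uninformative or that a false reassurance is likely, is not supported. This is a worthwhile improvement to an exploratory aim.

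**What to change.** Replace the logistic regression sentence under Aim 2 with wording such as:

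*For each specific AE, the worst severity recorded for a participant in each treatment week (0 = absent, otherwise the AE-log severity on the scale [state levels]) will be compared between SUVO and placebo within participant by an exact paired permutation test. Where grades are not too sparse, a Bayesian cumulative-logit mixed model will also be fitted in brms. Presence versus absence will be summarised by condition.*

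The log's severity scale must be written down, together with the weekly window and whether pre-existing complaints are logged in the placebo week. The permutation test uses complete pairs and does not adjust for period; the mixed model can carry a period term.

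The cost is modest drafting and programming, and brms is already in the plan. The drawbacks are some rater noise in severity and little gain for rare events.
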